## **8.2.5. Graphical Displays of Efficacy Endpoints**

A plot of geometric mean over time with bars for the 95% CI will be generated for quantitative urinalysis parameters (UA/C, UP/C, protein excretion, albumin excretion, urea, and creatinine). A plot of mean over time with bars for +/- the SE will be generated for eGFR and BP (Systolic and Diastolic separately). The FAS will be used.

## 9. SAFETY AND TOLERABILITY

Safety analyses will be based on the FAS. Descriptive statistics will be presented.

### 9.1. Adverse Events

AE data will be collected from the time that signed informed consent is obtained until the patient fully completes his/her participation in the study.

All AE summaries will be restricted to TEAEs, which are defined as any AE that newly appears, increases in frequency, or worsens in severity following the initiation of study medication, occurring during the treatment period. If it cannot be determined whether the AE is treatment-emergent due to a partial onset date, then it will be counted as treatment-emergent. Verbatim terms will be coded to PTs and SOC using MedDRA version 26.0.

Summaries that are displayed by SOC and PT will be ordered by descending order of incidence of SOC and PT within each SOC. Summaries of the following types will be presented:

- Overall summary of TEAEs.
- Patient incidence of TEAEs and the total number of entries by SOC and PT.
- Patient incidence of TEAEs and the total number of entries by PT in descending order.
- Patient incidence of TEAEs by SOC, PT, and highest severity. At each level of patient summarization, a patient is classified according to the highest severity if the patient reported 1 or more events. AEs with missing severity will be considered severe for this summary.
- Patient incidence and total number of entries of severe TEAEs by SOC and PT. AEs with missing severity will be considered severe for this summary.
- Patient incidence and total number of entries of study medication (Sparsentan) related TEAEs by MedDRA SOC and PT. Related AEs are those with relationships reported as “Possibly Related” or “Related”. AEs with a missing relationship will be considered related for this summary.
- Patient incidence and total number of entries of SGLT2 inhibitor related TEAEs by MedDRA SOC and PT. Related AEs are those with relationships reported as “Possibly Related” or “Related”. AEs with a missing relationship will be considered related for this summary.
- Patient incidence of serious TEAEs and the total number of entries by SOC and PT.
- Patient incidence of TEAEs leading to treatment discontinuation by SOC and PT.
- Patient incidence and total number entries of treatment-emergent AEOIs by SOC and PT.
- Patient incidence and total number of entries of TEAEs associated with safety topics of interest by PT.

- Patient incidence and total number of entries of related TEAEs associated with safety topics of interest by PT.
- Patient incidence and total number of entries of serious TEAEs associated with safety topics of interest by PT.

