9.3.2. Definition of Endpoint(s)

The safety endpoints include:

- Incidence of TEAEs, SAEs, AEs leading to treatment discontinuation, and AEOIs.
- Changes from baseline in body weight, vital signs, physical examinations, peripheral edema, and clinical laboratory parameters.

The primary efficacy endpoint is:

- The change from baseline in UA/C at Week 24.

The secondary efficacy endpoints are:

- Achievement of UA/C of <0.2 g/g at Week 24.

- Achievement of 30% and 50% reduction from baseline in UA/C at Week 24.
- Change from baseline in UA/C, UP/C, eGFR, and BP at each visit.

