#### **3.2.2. Safety Endpoints**

Safety endpoints include the following:

- The incidence of treatment-emergent adverse events (TEAEs), serious adverse events (AEs), AEs leading to treatment discontinuation, and adverse events of interest (AEOI).
- Changes from baseline in body weight, vital signs, physical examinations, peripheral edema, and clinical laboratory parameters.

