### **9.1.1. Adverse Events of Interest**

Abnormal liver function tests that meet the below criteria are considered AEOIs:

- The abnormality represents a new elevation in alanine aminotransferase (ALT) or aspartate aminotransferase (AST)  $>3 \times$  upper limit of normal (ULN), with or without an elevation of total serum bilirubin  $>2 \times$  ULN.
- The abnormality represents a 2-fold increase in ALT or AST above the baseline value in patients who had elevated values prior to starting study medication.

As described in [Section 9.1](#), patient incidence of treatment-emergent AEOIs occurring in the treatment period will be summarized.

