### **9.5.3. Incidence of Liver Function Abnormalities**

The incidence of patients (number and percentage of patients) with abnormalities in liver function tests (ALT, AST, alkaline phosphatase [ALP], and total bilirubin) post-baseline during the study will be summarized for the following categories:

- ALT and AST:
  - $>1 \times \text{ULN}$
  - $>2 \times \text{ULN}$
  - $>3 \times \text{ULN}$
  - $>5 \times \text{ULN}$
  - $>8 \times \text{ULN}$
- ALP:
  - $>1 \times \text{ULN}$
  - $>1.5 \times \text{ULN}$
  - $>2.5 \times \text{ULN}$
  - $>5 \times \text{ULN}$

- Total bilirubin:
  - $>1 \times \text{ULN}$
  - $>1.5 \times \text{ULN}$
  - $>2 \times \text{ULN}$
  - $>3 \times \text{ULN}$

Scatterplots of ALT vs AST, ALT vs total bilirubin, and AST vs total bilirubin maximum post-baseline values occurring during the study will be presented. If appropriate, evaluation of drug-induced serious hepatotoxicity plots of ALT or AST  $>3 \times \text{ULN}$  accompanied with total bilirubin by treatment group will be presented for assessment of potential drug induced liver injury. A listing of patients with  $>2 \times \text{ULN}$  total and  $>3 \times \text{ULN}$  ALT or AST at any time during the study will be provided.

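### SAE and AEOI incidence are endpoints without a time limit, but SAP 9.1 and 9.1.1 tabulate them for the treatment period only, so events starting in the 4-week follow-up reach listings alone

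*SAP*

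**What the plan says.** **Collection.** Protocol 8.5.1 collects AEs from consent to the follow-up visit. SAP 9.1 collects them until the participant completes the study.

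**Tabulation.** SAP 9.1 states: "All AE summaries will be restricted to TEAEs". A TEAE is an AE that newly appears, "increases in frequency, or worsens in severity following the initiation of study medication, occurring during the treatment period". The serious-event table is specified as "Patient incidence of serious TEAEs and the total number of entries by SOC and PT". SAP 9.1.1 repeats the limit: "patient incidence of treatment-emergent AEOIs occurring in the treatment period will be summarized". The protocol spells out the abbreviation TEAE but does not define it, so SAP 9.1 is the only definition.

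**Periods.** Protocol 1.1 (Study Arms and Duration) separates a 24-week treatment period from a 4-week follow-up period. Protocol 4.5 ends the treatment period at EOT, which is Week 24 or permanent discontinuation. Protocol Appendix 6, part B, labels Weeks 24 to 28 as non-treatment. SAP 4.1 describes the same 24 weeks on drug and 4 weeks off.

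**Endpoints.** Protocol 9.3.2 lists "Incidence of TEAEs, SAEs, AEs leading to treatment discontinuation, and AEOIs". SAP 3.2.2 lists "The incidence of treatment-emergent adverse events (TEAEs), serious adverse events (AEs), AEs leading to treatment discontinuation, and adverse events of interest (AEOI". SAP 5.3 declares no change from the protocol's planned analyses.

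**The concern.** Both endpoint lists name SAEs and AEOIs beside TEAEs as separate items, and neither limits them to treatment-emergent events. The SAP's tables apply that limit anyway. An SAE starting two weeks after the last dose would be collected and listed, yet would count in no incidence figure.

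Safety is a stated objective, and SAE and AEOI incidence are stated endpoints. As written, both would be reported over a narrower window than the endpoint implies, while SAP 5.3 says that nothing changed. The uncounted share of observation is largest in participants who stop early, and an adverse event is one of the listed reasons for stopping (Protocol 7.1).

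**Working it through.** **1. The plan's own figure.** SAP 4.3.1 gives 95% for at least one AE with N = 60 and 5% incidence. 1 − 0.95^60 = 95.4%, so it reproduces. No period is attached to the 5%, and it is a generic AE incidence, not an SAE or AEOI rate.

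**2. Tracing an SAE with a known onset two weeks after a Week 24 last dose.**
- Collected: yes (Protocol 8.5.1, SAP 9.1).
- TEAE: no, because onset falls after the treatment period.
- In the SAE table: no, since that table holds serious TEAEs.
- Elsewhere: by-patient listings (SAP 6.1, and SAP 9.1.2 if it meets a safety topic). The disposition table (SAP 7.1) shows it only if it is a reason for leaving the study.
- Exception: if a partial onset date leaves the status undecidable, SAP 9.1 counts the event as treatment-emergent. The gap therefore concerns known onsets.

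**3. Tracing a follow-up AEOI.** The liver table in SAP 9.5.3 covers values "post-baseline during the study will be summarized for the following categories".
- Criterion 1 (new ALT or AST >3×ULN): the value is counted there, though not as an AEOI.
- Criterion 2, "2-fold increase in ALT or AST above the baseline value in patients who had elevated values prior to starting study medication": there is no category for it. A baseline above 1.0 and up to 1.5×ULN that exactly doubles reaches above 2.0 and up to 3.0×ULN. It is counted only as >2×ULN.

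**4. Size of the window.** Share = f / (s + f), where s is the day of the last dose and f the days from last dose to the follow-up visit. f = 28 is nominal. The range 21 to 35 applies the ±7-day window of Protocol 1.3, which is an assumption for early stoppers, for whom Protocol 7.1 says only about 4 weeks.

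| Last dose | f = 28 | f = 21 to 35 |
|---|---|---|
| Day 168 | 28/196 = 14% | 11% to 17% |
| Day 84 | 28/112 = 25% | 20% to 29% |
| Day 28 | 28/56 = 50% | 43% to 56% |

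**5. Illustrative event counts (assumed rates).** Assume all 60 participants are followed for 4 weeks, with incidence p over T weeks at constant hazard. Let HR be the off-drug hazard divided by the on-drug hazard. Weekly hazard h = −ln(1 − p)/T; probability of an event in follow-up q = 1 − exp(−4 × h × HR); expected participants = 60q; chance of at least one = 1 − (1 − q)^60.
- p = 5%, T = 24, HR = 1: h = 0.002137, q = 0.00851, expected 0.51, chance 40%.
- p = 5%, T = 28, HR = 1: expected 0.44, chance 36%.
- p = 5%, T = 24, HR = 0.5 or 2: chance 23% or 64%.
- p from 2% to 10%, HR from 0.5 to 2, T = 24: chance 10% to 88%.

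**6. Where the end day is unclear.** Protocol 4.5 gives EOT as Week 24 or the time of permanent discontinuation. Protocol 7.1 places the early EOT visit only as near as possible to the last dose. An event between last dose and EOT visit could be classed either way. SAP 8.1 sets a 3-day rule after the last dose for efficacy, but SAP 9.1 has no counterpart for AEs.

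**The case against.** Protocol 9.3.3 states the planned analyses, and the AE tables it describes are TEAE tables by system organ class and preferred term, severity and relationship. SAP 9.1 delivers them. A reader might infer that the SAP departs from the protocol on AE analysis as a whole. It does not. This part of the objection stands, and it confines the mismatch to the SAE and AEOI endpoints.

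A reader might also infer that the treatment period has no end. Protocol 4.5 largely dates it, and only the days between last dose and EOT visit are open.

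For AEOIs, limiting the table to treatment is partly coherent. Protocol 8.5.7 ties these events to their relationship with study treatment, and the first step in Protocol Appendix 9 presupposes a participant on drug. ALT or AST >3×ULN in follow-up is still counted in SAP 9.5.3. What remains is mainly criterion 2. SAEs as such have no substitute table.

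Finally, the study is single-arm and descriptive, all data are listed, and every event rate above is assumed. That bears on the weight of the point. It does not close the gap: a listing is not an incidence, and incidence is the endpoint.

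**Conclusion.** The point holds for the SAE and AEOI endpoints, and it should be fixed. It rests on wording: the tables exclude known onsets after Week 24 or EOT, and the endpoints do not. The excluded window is 14% of post-dose AE collection for completers and more for early stoppers. The 40% and 36% figures depend on an assumed 5% incidence, constant hazard and complete follow-up. The 10% to 88% range shows how little the documents determine the count.

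A reader might infer that follow-up safety data are lost. They are not: events are listed, and laboratory, vital-sign, examination and edema results at Week 28 are summarized (SAP 9.5 to 9.7). A reader might also infer that the shift tables' last values, or the day-based laboratory windows, need on-treatment counterparts. The documents do not show these to be errors. Edema shifts are already given at each scheduled visit (SAP 9.7.1), and the other changes would be a matter of preference.

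**What to change.** 1. In SAP 9.1 state one TEAE end day, either last dose or EOT visit, and use it throughout the AE section. If the EOT visit is chosen, say what replaces it when no such visit took place.
2. Add one table of AEs, SAEs and AEOIs with onset after that day through the safety follow-up visit.
3. Add a row giving total SAE and AEOI incidence from first dose through that visit.
4. If any limit on the SAE or AEOI endpoints is kept, record it in SAP 5.3 as a change.

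The cost is SAP wording, one table and one row, with no new data. SAE and AEOI totals may rise slightly and include events after RAAS inhibitor treatment is restarted (Protocol 1.3, footnote g). The separate display makes those visible. The TEAE tables can otherwise stay as planned.

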### **9.1.1. Adverse Events of Interest**

Abnormal liver function tests that meet the below criteria are considered AEOIs:

- The abnormality represents a new elevation in alanine aminotransferase (ALT) or aspartate aminotransferase (AST)  $>3 \times$  upper limit of normal (ULN), with or without an elevation of total serum bilirubin  $>2 \times$  ULN.
- The abnormality represents a 2-fold increase in ALT or AST above the baseline value in patients who had elevated values prior to starting study medication.

As described in [Section 9.1](#), patient incidence of treatment-emergent AEOIs occurring in the treatment period will be summarized.

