10.5.1. Definition of AE

AE Definition

- An AE is any untoward medical occurrence in a clinical study participant, temporally associated with the use of study intervention, whether or not considered related to the study intervention.
- NOTE: An AE can therefore be any unfavorable and unintended sign (including an abnormal laboratory finding), symptom, or disease (new or exacerbated) temporally associated with the use of study intervention.

Definition of Unsolicited and Solicited AE

- An unsolicited AE is an AE that was not solicited using a participant diary and that is communicated by a participant who has signed the informed consent. Unsolicited AEs include serious and nonserious AEs.
- Potential unsolicited AEs may be medically attended (ie, symptoms or illnesses requiring a hospitalization, emergency room visit, or visit to/by a healthcare provider). The participants will be instructed to contact the site as soon as possible to report medically attended event(s), as well as any events that, though not medically attended, are of participant concern. Detailed information about reported unsolicited AEs will be collected by qualified site personnel and documented in the participant's records.
- Unsolicited AEs that are not medically attended nor perceived as a concern by the participant will be collected during an interview with the participants and by review of available medical records at the next visit.
- Solicited AEs are predefined local and systemic events for which the participant is specifically questioned, and which are noted by the participant in their diary.

Events Meeting the AE Definition

- Any abnormal laboratory test results (hematology, clinical chemistry, or urinalysis) or other safety assessments (eg, electrocardiogram (ECG), radiological scans, vital signs measurements), including those that worsen from baseline, considered clinically significant in the medical and scientific judgment of the Investigator (ie, not related to progression of underlying disease, or more severe than expected for the participant's condition).
- Exacerbation of a chronic or intermittent pre-existing condition including either an increase in frequency and/or intensity of the condition.
- New condition detected or diagnosed after study intervention administration even though it may have been present before the start of the study.
- Signs, symptoms, or the clinical sequelae of a suspected drug-drug interaction.

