10.8. Appendix 8: Recommendations for Management of Hyperkalemia

Serum potassium checks should be completed at each visit for clinical evidence of electrolyte imbalance. If a patient has a serum potassium value of >5.5 mEq/L (5.5 mmol/L) at any time during the study, the following steps are recommended:

1. If the serum potassium value is ≥ 6.5 mmol/L, emergency management should be implemented based on the site policies and Investigator's decision.
2. If the serum potassium value is >5.5 and <6.5 mmol/L, rule out measurement errors or likely reasons for the increase (eg, sample hemolysis, metabolic acidosis, discontinuation of diuretic by the patient/lack of compliance, diet transgression).
 - a. If the causes listed above are ruled out and the patient is not receiving a diuretic, it is recommended to start a diuretic (if the patient's volume status and BP permit). The choice of a thiazide or a loop diuretic is at the discretion of the Investigator. Assess the patient's tolerability and measure their BP, eGFR, sodium, and potassium within 1 week after starting the diuretic.
 - b. If the causes listed above are ruled out and the patient is already receiving a diuretic, increase the dose of the diuretic by 50% (if the patient's volume status and BP permit). Assess the patient's tolerability and measure their BP, eGFR, sodium, and potassium within 1 week after increasing the dose. Consider correction of metabolic acidosis, if relevant.
3. In both scenario 2a and 2b, adjust the dose of diuretic accordingly after 1 week. If the patient's serum potassium value is still >5.5 mEq/L (5.5 mmol/L), reinforce diet counseling/restrictions, rule out other potential causes of hyperkalemia, and consider increasing the diuretic dose. If, after an additional week, the serum potassium value is still >5.5 mEq/L (5.5 mmol/L), reduce the dose of study intervention by 50%. For long-term prevention of hyperkalemia, consider treatment with patiromer or sodium zirconium cyclosilicate.
4. If hyperkalemia persists or recurs, study intervention must be discontinued permanently.

10.9. Appendix 9: Liver Safety: Suggested Actions and Follow-up Assessments and Study Intervention Rechallenge Guidelines

Abnormal liver function test results that meet at least one of the following criteria below will be considered AEOIs and must be reported to the Sponsor's Medical Monitor within 24 hours of awareness:

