- The abnormality represents a new elevation in ALT or AST >3 times ULN, with or without an elevation of total serum bilirubin >2 times ULN.
- The abnormality represents a 2-fold increase in ALT or AST above the baseline value for the study period (ie, Day 1) in participants who had elevated values prior to starting study intervention.

In such instances, the following steps should be taken:

1. Temporarily discontinue study intervention.
2. Perform repeat testing of ALT, AST, liver specific alkaline phosphatase (ALP), and total bilirubin within 48 to 72 hours to confirm the abnormalities.
3. If the abnormality is confirmed by repeat results, the following should be done:
 - a. Complete an AEOI Report Form that documents both the liver function test findings and any associated signs or symptoms, and report by email to the SAE contact on the SAE Contact Information page ([Section 10.1.1](#)) of this protocol.
 - b. Monitor liver enzymes and serum bilirubin 2 or 3 times weekly. The frequency of retesting can decrease to once weekly or less if the abnormalities stabilize and the participant is asymptomatic.
 - c. Perform additional testing to evaluate liver function, as appropriate (eg, INR and direct bilirubin).
4. Do not resume study intervention until monitoring indicates abnormalities have resolved or stabilized.

Participants are not allowed to resume study intervention if they have the following:

- ALT or AST >8 times ULN.
- ALT or AST >5 times ULN for more than 2 weeks.
- ALT or AST >3 times ULN and total bilirubin >2 times ULN or INR of >1.5 .
- ALT or AST >3 times ULN, with symptoms of fatigue, nausea, vomiting, right upper quadrant pain or tenderness, fever, rash, and/or eosinophilia ($>5\%$ eosinophils).

Management of such participants should be closely coordinated with the Sponsor's Medical Monitor. In addition to monitoring liver function tests, the Investigator should perform other relevant clinical and laboratory measurements to identify potential causes of the abnormalities (eg, acute viral hepatitis types A, B, C, D, and E; autoimmune or alcoholic hepatitis; nonalcoholic steatohepatitis; biliary tract disease or exposure to hepatotoxic medications or environmental chemical agents). Additionally, participants who demonstrate elevated liver enzymes a second time after re introduction of the study intervention may continue in the clinical study; however, they will not receive study intervention for the remainder of the trial.

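### Liver AEOIs are defined by laboratory value but tabulated as coded adverse events, with no rule for deriving them from the laboratory data

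*SAP*

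**What the plan says.** Protocol 9.3.2 lists the safety endpoints as "Incidence of TEAEs, SAEs, AEs leading to treatment discontinuation, and AEOIs".

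Both documents define an AEOI by laboratory result. Protocol 10.9 (Appendix 9) states: "Abnormal liver function test results that meet at least one of the following criteria below will be considered AEOIs". SAP 9.1.1 states: "Abnormal liver function tests that meet the below criteria are considered AEOIs". There are two criteria:

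- Criterion 1 is a new ALT or AST elevation above 3 x ULN, with or without raised bilirubin.
- Criterion 2 is "a 2-fold increase in ALT or AST above the baseline value in patients who had elevated values" before treatment.

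The handling of such results is spread over several sections:

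- Protocol 8.5.7 and 10.9 require notice to the Medical Monitor within 24 hours, without waiting for a repeat.
- Protocol 10.9, step 3, opens with "If the abnormality is confirmed by repeat results, the following should be done", and its first item is "Complete an AEOI Report Form that documents both the liver function test findings and any associated signs or symptoms". That form goes by email to the SAE contact.
- Protocol 8.5.7 also has an AESI form in the eCRF. It applies when a reported AE or SAE meets the criteria.
- Protocol 10.5.1 makes a laboratory abnormality an AE when it is "considered clinically significant in the medical and scientific judgment of the Investigator". Protocol 8.4.4 follows the same principle.

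SAP 9.1 restricts all AE summaries to TEAEs and lists this output: "Patient incidence and total number entries of treatment-emergent AEOIs by SOC and PT". SAP 9.1.1 refers back to that summary and adds no derivation.

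**The concern.** The definition is objective and rests on laboratory values. The planned output is organized by SOC and PT, which come from coded AE terms. Between the two stands the decision to record an AE, and that rests on the investigator's view of clinical significance. A value can meet the definition and still have no term to tabulate.

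Transaminase elevation is the first entry in the protocol's risk table, and the AESI section is devoted to liver safety. In a single-arm study of about 60 participants one case is visible in the result, and this gap can only lower the count. The laboratory tables would matter less as a backstop if they reproduced both criteria, so they need checking too.

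**Working it through.** **1. Definition against count.**

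| Step | Source | Condition |
|---|---|---|
| Value is an AEOI | Protocol 8.5.7, 10.9; SAP 9.1.1 | Meets either criterion |
| Medical Monitor notified | Protocol 8.5.7, 10.9 | Meets either criterion |
| AEOI Report Form emailed | Protocol 10.9, step 3 | Repeat confirms |
| AESI form in eCRF | Protocol 8.5.7 | An AE or SAE has been reported |
| Laboratory value becomes an AE | Protocol 8.4.4, 10.5.1 | Judged clinically significant |
| AEOI tabulated | SAP 9.1 | TEAE with SOC and PT |

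The last row depends on the one above it. The eCRF form does not bypass it, because it too starts from a reported AE or SAE. Nothing in the SAP ties the count to the emailed form.

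**2. What the laboratory tables show.**

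- SAP 9.5.3 counts ALT and AST above 1, 2, 3, 5 and 8 x ULN. The >3 row holds the values that meet the criterion 1 threshold. It is not the AEOI count: it does not ask whether the elevation is new, and it covers the study rather than the treatment period.
- The normal-range shift table (SAP 9.5.1) shows high to high, which does not reveal a doubling.
- The CTCAE shift table (SAP 9.5.2) cannot be checked, since the documents do not give its grade boundaries.
- Absolute and percentage changes (SAP 9.5) are group summaries.
- The liver listing in SAP 9.5.3 needs bilirubin above 2 x ULN together with ALT or AST above 3 x ULN.

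**3. Criterion 2 on the ULN scale.** Protocol exclusion 5 rules out ALT or AST above 2 x ULN at screening, so values above ULN and up to 2 x ULN can enter. Assume that elevated means above ULN (the documents do not define it) and that the value exactly doubles:

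value = 2 x baseline

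| Baseline (x ULN) | Doubled (x ULN) | In >2 row | In >3 row |
|---|---|---|---|
| 1.01 | 2.02 | yes | no |
| 1.2 | 2.4 | yes | no |
| 1.5 | 3.0 | yes | no |
| 1.6 | 3.2 | yes | yes |
| 2.0 | 4.0 | yes | yes |

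A baseline above 1 and up to 1.5 x ULN gives an AEOI that is missing from the >3 row. It is present in the >2 row, but mixed there with participants who did not double.

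**4. Size.** The plan's own figure (Protocol 9.5) is a 95% chance of at least one event with n = 60 and 5% incidence:

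1 - (1 - 0.05)^60 = 0.954, which reproduces it.

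Let c be the share of qualifying participants who have an AE record. The chance of tabulating at least one AEOI is 1 - (1 - p x c)^60, and the expected count is 60 x p x c. Both p and c are assumptions; the documents give neither for AEOIs.

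| c | p = 5%: chance, expected count | p = 2%: chance, expected count |
|---|---|---|
| 100% | 0.954, 3.0 | 0.702, 1.2 |
| 90% | 0.937, 2.7 | 0.664, 1.08 |
| 75% | 0.899, 2.25 | 0.596, 0.9 |
| 50% | 0.781, 1.5 | 0.453, 0.6 |

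**The case against.** The best defense is that the specific rule governs the general one. A qualifying result is designated an adverse event of interest outright, with no judgment attached. Protocol 10.9 also attaches a treatment interruption and repeat testing to it, and Protocol 6.5 has dosing dates recorded. A value with those consequences is unlikely to go unrecorded. The display by SOC and PT does not say where the AEOI flag comes from. The study is descriptive, and no decision threshold hangs on AEOI incidence.

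Much of this stands. An unrecorded value may be uncommon, and reading the count as AE-based is an inference from SAP 9.1, not something the SAP states. But no sentence in either document requires every qualifying value to be entered as an AE, and the SAP is silent on the source of the flag. For a named endpoint, that silence is the defect.

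A reader might infer three stronger things, which the documents do not support:

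- *That the confirming repeat decides what is counted.* It governs the emailed AEOI Report Form. The eCRF form has no repeat condition, and the SAP refers to neither form.
- *That qualifying values disappear.* The Medical Monitor is to be notified, SAP 6.1 lists individual data, and SAP 9.5.3 counts values above 3 x ULN. Under the assumption above, criterion 2 doublings also fall in its >2 row.
- *That no laboratory table captures criterion 2 at all.* Since the CTCAE boundaries are not given, the most that can be said is that no table explicitly isolates it.

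**Conclusion.** The point holds as a gap between the definition of a named safety endpoint and its planned count. As written, AEOI incidence can omit a participant who meets the definition but has no AE record, and the direction is undercounting.

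The size is unknown. The documents do not say how many participants will have elevated baselines, how many will double, or how many qualifying values will lack an AE record. One participant is 1/60 = 1.7 percentage points, but that is the unit of the result and not an estimate of the effect. The probabilities above are illustrations under assumed incidence and capture.

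The conclusion rests on reading SAP 9.1 as a tabulation of AE records. The criterion 2 arithmetic rests on elevated meaning above ULN and on an exact doubling. It is an inexpensive improvement that should be made before database lock.

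**What to change.** In the SAP:

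- In 9.1.1, derive AEOI incidence in the treatment period from the laboratory data with both stated criteria. Include unscheduled results and any recorded local results. Say explicitly that the one-value-per-window selection in 6.5.3 and the central-laboratory-only rule in 6.6.2 do not limit this derivation.
- Define an elevated baseline: the threshold, and which pretreatment value it uses.
- Show the derived count next to the AE-based count, and list participants on whom the two disagree.
- In 9.5.3, add a row for a 2-fold rise over an elevated baseline.

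Across documents, the sponsor should reconcile Protocol 8.5.7, Protocol 10.9 and SAP 9.1.1 on whether the endpoint counts any qualifying value or only confirmed ones. This concerns what is counted and proposes no change to clinical management.

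The cost is one derived table, one added row and some wording, all from data already planned for collection. The reported incidence may rise.
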